11.4 Statistical criteria of termination of trial

No such criteria are defined.

11.5 Planned Analyses

11.5.1 Primary Analysis

The primary endpoint of this study is the SIA score as described in Dai et al.¹⁴. The SIA score integrates total morphine consumption in mg within the first 24 hours post surgery and Pain (VAS) in the first 24 hours after surgery. Pain is assessed several times. The average of all measurements taken in a patient will be used to calculate the SIA score.

The SIA score will be analyzed in a linear model. Treatment arm will be included as two-level factor ("lidocaine" vs "placebo"). Duration of surgery and number of trocars will be included as covariates.

Model validation will be performed by checking residuals and leverages. The residuals will be checked by visual inspection using a plot of the residuals vs the fitted values and a Normal Q-Q plot. In case of substantial violations of model assumptions, transformations or the use of a generalized linear model will be considered. The estimated treatment effect, the 95% confidence interval thereof and the p-value will be presented. The analysis will be performed using $\alpha=0.05$ (two-sided).

The analysis will be performed on the ITT set.

A sensitivity analysis will be performed on the PP analysis set and compared to the main analysis in order to investigate the influence of protocol deviations.

[figure not shown]

Figure 1: The total number of evaluable patients (both arms together, on the y-axis) required to reach different levels of power (separate lines), given a range of true effect sizes in terms of theta (x-axis). The figure is based on simulations, where in each simulation, the treatment effect on morphine use was set to theta and the effect on pain to $0.75 \cdot \theta$.

11.5.2 Secondary Analyses

Endpoints Secondary endpoints comprise:

Morphine consumption: morphine consumption within the first 48 hours post surgery in mg.

Pain intensity: measured using a visual analogue scale (VAS), measured up to 6 months after skin closure..

Time to hospital discharge: The duration of hospital stay will be defined as the time in days from the date of surgery until the date of discharge from hospital in days.

Pain intensity and morphine consumption are measured at 1, 2, 4, 8, 16, 24, and 48 hours after skin closure. Pain is additionally measured after 2 weeks as well as 3 and 6 months after skin closure.

Method of analysis

All secondary analyses will be performed on the ITT analysis set. However, patients with missing value in a secondary endpoint will not be included in the corresponding analysis. No imputations for the secondary endpoint will be performed.

To decompose the effect on SIA as studied in the primary analysis, we analyze the treatment effect ("lidocaine" vs "placebo") on pain and morphine consumption during the first 24 hours also as separate variables. Duration of surgery and number of trocars will be included as covariates. In case of substantial violations of model assumptions, we will use a poisson model. In case of over dispersion a negative binomial model will be used.

Time to hospital discharge will be analysed in a Cox-proportional hazards model. Treatment arm will be

included as two-level factor ("lidocaine" vs "placebo"). Duration of surgery and number of trocars will be included as covariables.

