5.2 Secondary Outcomes

- Pain intensity (VAS) and total morphine consumption at 1, 2, 4, 8, 16, 24 and 48 hours after skin closure. Length of hospital stay – Defined as the time (in days) from the date of surgery until the date of discharge.
- Time to first defecation – Defined as the time from skin closure to the time of first defecation.
- Occurrence of nausea and/or vomiting
- Chronic pain – pain intensity (VAS) will be assessed (with and without coughing) 2 weeks (+2 weeks), 3 and 6 months (\pm 7 days) after surgery

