9.2.2 Assessment of secondary outcomes

Pain and morphine consumption

Pain intensity using the VAS and total morphine consumption will be recorded 1, 2, 4, 8, 16, 24 and 48 hours after skin closure.

Nausea and vomiting

On arrival in the PACU the patient will be asked if they are nauseous.

The patients will be instructed to inform the staff of any nausea or vomiting that they may experience.

First defecation

Once on ward, the patients will be questioned at timepoints 1 hr, 2 hrs, 4 hrs, 8 hrs, 16 hrs, 24 hrs and 48 hrs after skin closure regarding their bowel movements and the patients will be instructed to inform the staff of their first defecation.

The approximate time of the first defecation will be recorded in the CRF.

Length of hospital stay

Defined as time from surgery until patients are discharged from the hospital

Chronic pain assessment

During follow up at 2 weeks (+2 weeks), 3 and 6 months (± 7 days), patients will be assessed for pain intensity (VAS 1 to 10) while being immobile and while coughing, pain experience (no pain, mild, discomforting, distressing, horrible, excruciating) and for the sensory and affective dimension of pain with the short-form McGill Pain Questionnaire

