9.3.4 Data of patient-controlled analgesia (PCA)

- Total morphine consumption (mg)
- Total PCA requests
- Positive PCA requests
- Negative PCA requests
- Pain intensity (VAS Score) – with coughing and when immobile
- Riker sedation agitation scale¹⁸PONV [nausea, present or not; vomiting, number of events]
- Adverse events of lidocaine infusion (light headedness, drowsiness, perioral numbness, visual disturbances, metal taste)
- Additional analgesic medication including dose and time of intake during the hospital stay

9.3.5 Hospital stay and follow up data (postoperative day 1 and 2, follow up 2-4 weeks, 3 and 6 months later)

Daily ward rounds until discharge by the surgeon and his delegates to assess the patient for complications. Follow up is performed by the surgeon and the study coordinator during the visit at our outpatient clinic or per telephone inquiry

- Date of discharge from the hospital (day/month/year)
- Pain intensity [VAS Score] – with coughing and when immobile
- Additional analgesic medication including dose and time/date of intake during the hospital stay

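### Read literally, the complete-case rule for secondary endpoints drops patients with no recorded first defecation, who tend to be the slowest, so a real difference between arms is attenuated by an unknown amount

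*Protocol*

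**What the plan says.** Time to first defecation is a secondary outcome in the synopsis and in sections 4.3 and 5.2. Section 5.2 gives it no upper limit and no rule for a patient in whom the event is not seen: "Defined as the time from skin closure to the time of first defecation".

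Section 9.2.2 describes two ways of capturing it. Ward patients are questioned at set times, the last being "24 hrs and 48 hrs after skin closure regarding their bowel movements". In addition, "the patients will be instructed to inform the staff of their first defecation", with no stated end. On recording, the section says only: "The approximate time of the first defecation will be recorded in the CRF". Nothing is said about what is entered when there has been no event.

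Section 9.3.5 adds "Daily ward rounds until discharge by the surgeon and his delegates to assess the patient for complications". The items it lists for the hospital stay and follow-up are discharge date, pain intensity and additional analgesics. Bowel function is not among them.

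Section 11.5.2 then sets one rule for all secondary analyses: "patients with missing value in a secondary endpoint will not be included in the corresponding analysis". It adds: "No imputations for the secondary endpoint will be performed". Its own endpoint list names morphine consumption, pain and time to discharge, but not time to first defecation. The only time-to-event model is for discharge: "Time to hospital discharge will be analysed in a Cox-proportional hazards model".

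**The concern.** A gap in this endpoint is not like a missed pain score. The value exists only if the event happens and is noted while someone is still in a position to note it, so the patients without a value tend to be those with long times. A rule that removes them selects on the outcome after randomisation, and randomisation no longer protects the comparison. Both arms are cut back towards their early responders, estimated times are too short, and the contrast between arms shrinks.

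A second route runs through discharge. Section 3.1 hypothesises that lidocaine shortens stay. If it does, patients in the two arms are observed for different lengths of time, and the share excluded may differ by arm.

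At stake is one secondary outcome, although one of the benefits that section 3.7 puts forward for lidocaine. The primary analysis is untouched.

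**Working it through.** **Inputs from the protocol.** Complete-case rule and no imputation (11.5.2); last scheduled bowel question at 48 h and open-ended self-report (9.2.2); 1:1 allocation (6.2.1); 42 evaluable patients, 21 per arm (11.3); two-sided 0.05, stated for the primary analysis (11.5.1). The protocol states no figure for this endpoint that could be reproduced. The 21 per arm was set for the primary endpoint and serves here only as a realistic size. Its recruitment figure roughly checks: 42/0.70 = 60, against 59 stated.

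**Assumed inputs.** The protocol gives no defecation times, so a range was used. Distributions were lognormal (sigma 0.5), exponential, and Weibull (shape 2). Medians for placebo vs lidocaine were 30/20, 36/24, 48/36, 48/24, 60/48, 60/36 and 72/48 h.

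**Closed-form check.** For exponential times with median m, the share later than 48 h is S = 2^(−48/m). The median among those at or before 48 h is the t that solves 1 − 2^(−t/m) = (1 − S)/2.

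- m = 60: S = 0.574; (1 − 0.574)/2 = 0.213; t = 20.7 h.
- m = 48: S = 0.500; (1 − 0.500)/2 = 0.250; t = 19.9 h.

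If every time after 48 h is lost, a 12 h difference in medians becomes about 0.8 h. The simulation gives the same 0.8 h. On means, the difference goes from 60/ln 2 − 48/ln 2 = 86.6 − 69.2, about 17.3 h, to 21.8 − 21.2, about 0.5 h. Medians must be compared with medians and means with means.

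**Simulation.** Median differences come from 400,000 draws per arm. Power is for a log-rank test with 21 per arm, from 1,500 repetitions (Monte Carlo standard error at most √(0.25/1500) ≈ 0.013). Selected rows:

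| Distribution, medians (h) | Later than 48 h, placebo / lidocaine | True median difference (h) | Left if all late times are lost | Left if half are captured | Power: full / censored at 48 h / dropped |
|---|---|---|---|---|---|
| Lognormal 30 vs 20 | 17% / 4% | 10.0 | 7.4 h (74%) | 87% | 0.68 / 0.67 / 0.45 |
| Lognormal 36 vs 24 | 28% / 8% | 12.0 | 7.2 h (60%) | 80% | 0.67 / 0.66 / 0.32 |
| Lognormal 48 vs 36 | 50% / 28% | 12.0 | 4.2 h (35%) | 67% | 0.43 / 0.39 / 0.10 |
| Lognormal 60 vs 36 | 67% / 28% | 24.0 | 6.8 h (28%) | 65% | 0.86 / 0.80 / 0.20 |
| Lognormal 72 vs 48 | 79% / 50% | 24.0 | 4.1 h (17%) | 92% | 0.68 / 0.55 / 0.07 |
| Weibull 60 vs 36 | 64% / 29% | 24.0 | 3.4 h (14%) | 59% | 0.88 / 0.64 / 0.09 |
| Exponential 48 vs 24 | 50% / 25% | 24.2 | 3.7 h (15%) | 52% | 0.57 / 0.44 / 0.07 |
| Exponential 72 vs 48 | 63% / 50% | 23.6 | 1.4 h (6%) | 46% | 0.27 / 0.15 / 0.07 |

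Across all 21 scenarios, 6% to 74% of the median difference remains if every late time is lost, and 46% to 92% if half are captured, equally in both arms. Every scenario moves towards no difference, but all use the same cut-off in both arms. Discharge that differs by arm was not modelled.

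The censored column stops everyone at 48 h. It therefore understates the proposed analysis, which would also use the late times that patients report.

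**The case against.** Three objections have force.

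First, a reader might infer that recording stops at 48 h. It does not. Self-report has no end time, and the synopsis lists time to first defecation among the items taken from the medical records. An inpatient's event at 60 h can be recorded. Values are lost mainly when the patient is discharged first or does not report. This stands, and it makes the columns with every late time lost an extreme case.

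Second, section 11.5.2 neither lists this endpoint nor says whether no event by last contact is missing or censored. The protocol leaves detailed methods to a statistical analysis plan that is not shown here, so the absence of a model or a censoring rule is not in itself a fault. That also stands. What remains is a rule the protocol does state, for all secondary analyses and without exception for unobserved events. An analysis plan that censored these patients would depart from its literal wording, and section 11.5.4 asks for deviations to be listed and justified, with an amendment if substantial.

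Third, a reader might infer that a true difference would be largely erased. The documents do not support this, because they give neither defecation times nor the share of late patients. Near-total loss needs slow medians and little or no capture after 48 h; with faster medians most of the difference survives.

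An arm-dependent bias from shorter stay is likewise only a possibility. It depends on how far lidocaine moves discharge relative to defecation, for which there are no figures.

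**Conclusion.** The concern holds in a limited form. Taken at its word, the rule in 11.5.2 makes inclusion in the analysis of time to first defecation depend on the outcome. A real difference is then generally attenuated, by an amount the documents do not determine. The 6% to 74% and 46% to 92% ranges illustrate the possible size; they rest on assumed medians, assumed shapes and a common 48 h cut-off, and are not estimates for this trial.

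Neither a hard stop at 48 h nor a known direction of bias between arms can be read from the protocol. This should be corrected because the rule is stated and the remedy is nearly free, but it concerns one unpowered secondary endpoint and leaves the primary result unaffected.

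**What to change.** In section 11.5.2:

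- Add time to first defecation as a time-to-event endpoint, analysed with the Cox model already specified for discharge (treatment arm, duration of surgery, number of trocars).
- Censor a patient without a recorded event at the last bowel assessment or at discharge.
- State that a censored patient does not count as missing under the exclusion rule.

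The cost is a few sentences in the protocol or analysis plan. No new data are needed, since discharge date is already collected under 9.3.5. One small drawback is that discharge may be related to recovery, so censoring there may be somewhat informative. It still keeps information that exclusion discards.

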3. BACKGROUND AND RATIONALE

3.1 Background and Rationale

Pain after thoracic surgery is associated with alterations in lung function, potentially leading to pulmonary complications (e.g., atelectasis, pneumonia) and thus increased perioperative morbidity¹. Furthermore, thrombosis, endocrine and cardiac complications are the consequences of insufficient treated postoperative pain (2-4). Optimized perioperative pain management, therefore, is paramount² especially in times of fast-track surgery, as patients are scheduled for discharge at the earliest possible time after abdominal surgery³. The administration of lidocaine perioperatively in open abdominal or laparoscopic abdominal surgeries where general anaesthesia is required, has been associated with decreased postoperative pain, faster recovery of bowel function, fewer opioid side effects and a shortened hospital stay^{4,5}. However, although the perioperative administration of lidocaine seems advantageous in (some cases of) laparoscopic interventions, a recent study examining the effects of lidocaine in laparoscopic renal surgery found no such benefits⁶. Further, studies in orthopedic surgery, cardiac surgery or otorhinology showed no benefit either⁷⁻⁹. Because beneficial findings stem from laparoscopic interventions in the peritoneal cavity, a similar effect for interventions in the thoracic cavity may be postulated. Recently, Slovack et al. showed no effect of lidocaine in thoracic surgery but their population size was small and the morphine consumption in the control group was lower than has been shown in other groups¹⁰.

At the University Hospital Basel, the current standard of care for thoracoscopic interventions does not include the perioperative administration of lidocaine. Thus examining the benefits of intravenous treatment with lidocaine is of great interest to patients and surgeons and may lead to better postoperative pain management and less postoperative complications.

Therefore we hypothesize that the perioperative administration of lidocaine will lead to a decreased postoperative pain, shorter hospital stays, decreased development of chronic pain and decreased 30-day mortality.

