3.8 Justification of choice of study population

We include all patients undergoing video-assisted thoracoscopic procedures, with planned operation time less than 90 minutes e.g. wedge resection, pneumothorax, small nodules in the lung parenchyma, under general anaesthesia, who have an American Society of Anaesthesiologists [ASA] physical status class I to III. Vulnerable patients (children, patients with cognitive impairment and patients with documented dementia) will be excluded from the study. We are interested in the effect of Lidocaine on post-operative pain in thoracic surgery patients because pain could lead to other morbidities.

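### Patients discharged before 48 h would be dropped from the 48 h pain comparison, which would bias it towards no difference if discharge follows recovery

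*Protocol*

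**What the plan says.** Protocol section 11.5.2 places all secondary analyses on the ITT set and then sets the rule for missing data: "patients with missing value in a secondary endpoint will not be included in the corresponding analysis", and "No imputations for the secondary endpoint will be performed".

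The endpoints under that rule include "morphine consumption within the first 48 hours post surgery in mg". Section 5.2 lists "Pain intensity (VAS) and total morphine consumption at 1, 2, 4, 8, 16, 24 and 48 hours after skin closure". The pain and morphine model written out in 11.5.2 covers only the first 24 hours; no 48 h model is given.

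The schedule (section 9.3) puts the 48 h reading in the ward block, and the next planned pain assessment is at day 14. Sections 9.3.4 and 9.3.5 record additional analgesics during the hospital stay only. Section 8.5, on withdrawn participants, says there are no study-specific follow-up visits. No rule covers a patient discharged before 48 h.

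Section 3.8 describes the population as patients "with planned operation time less than 90 minutes e.g. wedge resection, pneumothorax, small nodules in the lung parenchyma". Section 3.1 hypothesises that "perioperative administration of lidocaine will lead to a decreased postoperative pain, shorter hospital stays".

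**The concern.** Whether a patient is still on the ward at 48 h is decided after randomisation, and the Protocol itself expects lidocaine to change it. Keeping only patients who have a 48 h reading may then select on a variable linked both to arm and to pain. If patients with less pain leave sooner, those who remain are the ones with more pain, and the selection is stronger in the arm that does better. Describing the set as ITT does not prevent this, because the exclusion is applied afterwards, endpoint by endpoint.

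At stake is the reading of the 48 h result: an effect that lasts to 48 h could be reported as having faded, with fewer patients contributing to the comparison.

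**Working it through.** **The plan's own figures.** The Protocol states no length of stay and no share discharged before 48 h, so no figure on this point can be reproduced. The sample size behind the check is 42 evaluable patients, 21 per arm (11.3). Inflating for 30 % drop-out gives 42/0.70 = 60 against 59 stated, and 55/0.70 = 78.6, so 79 as stated.

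**Inputs from the Protocol (11.2, 11.3).** Pain SD σ = 1.91; pain effect δ = 1.5; 21 per arm. The SD and effect are planning values for the 24 h endpoint. Using them at 48 h is an assumption.

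**Assumptions not in the documents.** The share discharged before 48 h, and how strongly discharge depends on pain.

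**Route 1: large-sample bias.** Give each patient a tendency to leave that has correlation −ρ with 48 h pain within arm, and let the patient leave when it exceeds a threshold c. Lidocaine acts on discharge only through pain, so its threshold is c − ρδ/σ. With λ(x) = φ(x)/Φ(x), the difference among patients with a reading is

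δ − σρ[λ(c_lidocaine) − λ(c_placebo)].

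Example with 20 % missing overall and ρ = 0.6:
- ρδ/σ = 0.6 × 1.5/1.91 = 0.471.
- The thresholds are 1.101 for placebo (13.6 % leave) and 0.630 for lidocaine (26.4 % leave).
- λ is 0.252 and 0.445.
- The difference is 1.5 − 1.91 × 0.6 × (0.445 − 0.252) = 1.28.

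A simulation of 400,000 patients gives the same unadjusted 1.28. It gives 1.32 from a linear model with arm and one simulated covariate, a loss of 0.18/1.50 = 12 %.

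| Situation, 20 % missing | 48 h pain difference, adjusted (true 1.5) |
|---|---|
| Discharge unrelated to pain | 1.5 |
| Discharge driven by a modelled covariate | 1.5 |
| ρ = 0.3 | 1.45 |
| ρ = 0.6 | 1.32 |
| ρ = 0.6, lidocaine patients leave more often at equal pain | 1.15 |
| ρ = 0.6, lidocaine patients leave less often at equal pain | 1.71 |
| Discharge fully determined by 48 h pain | 0.98 |

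With 10-20 % missing and ρ of 0.3-0.6, the adjusted loss is about 2-12 %.

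**Route 2: trials of the planned size.** Simulate 21 per arm, with discharge depending on 24 h pain through a logistic model. Assume 10-30 % of placebo patients leave before 48 h and a 24 h to 48 h correlation of 0.6-0.8.
- Log-odds of 1 to 2 per SD: about 6 to 17 of 42 patients are dropped. The estimate falls from 1.50 to 1.12-1.42, a loss of up to (1.50 − 1.12)/1.50 = 25 %. Power of a 48 h pain comparison falls from about 70 % to 33-59 %. Repeat runs agree closely (lowest estimate 1.08).
- Log-odds of 0.25 to 0.5 per SD: 1.44-1.49, a loss of at most 4 %.

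The lowest estimates need 30 % placebo discharge and log-odds 2, which implies that about 53 % of lidocaine patients leave before 48 h.

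A likelihood estimator that also uses 24 h pain returns 1.49-1.52 with 47-66 % power. That recovery is built in, because discharge was simulated to depend only on the observed 24 h value. It shows that the method works under that condition, not that the condition holds.

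**The case against.** A reader might infer that the plan certainly removes the fastest-recovering patients and so certainly understates a lidocaine benefit. The documents do not support that. A planned operation time under 90 minutes is not a length of stay, and the schedule expects the patient to be on the ward at 48 h. The direction is conditional too: there is no bias if discharge is unrelated to pain, and overstatement if lidocaine patients leave less often at equal pain. That last mechanism runs against the trial's own hypothesis but cannot be excluded.

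Three other stronger readings also fail:
- **Morphine is affected in the same way.** The pump records use (9.2.1), so the inpatient total may be known up to removal and need not be missing. The Protocol simply does not say whether it then counts as a complete 48 h value.
- **The earlier readings are discarded.** They still enter the primary score and the separate 24 h pain and morphine analyses. They are unused only in the 48 h comparison.
- **The effect at 48 h will be 1.5 points.** The infusion ends 2 hours after skin closure, so carrying the 24 h effect forward is a working assumption.

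Two defences of the plan carry less weight. The synopsis promises a sensitivity analysis on all patients with multiple imputation, but it names no endpoint and conflicts with "No imputations for the secondary endpoint will be performed". The analysis plan, which is not shown, may specify a 48 h model. The exclusion rule is nevertheless fixed in the Protocol and, as worded, would still drop anyone without a 48 h value.

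**Conclusion.** The concern holds in conditional form. The Protocol fixes complete-case analysis for a ward-based 48 h pain reading, plans no way to obtain it after discharge, and hypothesises that treatment shortens stay. If discharge follows recovery, the 48 h pain comparison is biased towards no difference and loses precision.

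The size cannot be determined from the documents. It is about 2-12 % attenuation under modest assumptions, about 25 % under strong ones, and nil if discharge is unrelated to pain, all with the 24 h SD and effect carried to 48 h. More extreme discharge mechanisms give larger losses, but nothing in the Protocol points to them.

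The matter concerns one time point of a secondary endpoint. The 24 h primary analysis is untouched. The rule should be changed because a better one uses data already collected, but it does not threaten the trial's main conclusion.

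**What to change.** In section 11.5.2:
1. Analyse in-hospital pain from 1 to 48 h in one linear mixed model for repeated measures, with arm, time, arm by time, duration of surgery and number of trocars. Take the 48 h contrast from it. Patients with earlier readings then contribute without imputation, and the exclusion rule no longer applies to this endpoint.
2. State that a patient off the pump or discharged before 48 h is not counted as missing for inpatient morphine. The total is the pump total plus other recorded inpatient opioid.
3. Report by arm the number discharged before 48 h, so that readers can judge how far the 48 h result depends on early discharge.
4. Reconcile the multiple-imputation sensitivity analysis in the synopsis with the no-imputation rule, and name the endpoint it applies to.

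The cost is a few lines and a standard model, with no new data. There are two limits: the mixed model assumes that missingness depends on recorded readings, and opioid taken at home before 48 h is not counted.
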